Abdominal wound dehiscence (also referred to as 'evisceration' or 'fascial dehiscence'). Defined as an unintended acute wound failure at the level of the fascia and a postoperative complication after primary closure of a laparotomy incision.

Degree of contamination during surgery

Clean: an incision in which no inflammation is encountered in a surgical procedure, without a break in sterile technique, and during which the respiratory, alimentary and genitourinary tracts are not entered

Clean-contaminated: an incision through which the respiratory, alimentary or genitourinary tract is entered under controlled conditions but with no contamination encountered

Contaminated: an incision undertaken during an operation in which there is a major

break in sterile technique or gross spillage from the gastrointestinal tract, or an incision in which acute, non-purulent inflammation is encountered. Open traumatic wounds that are more than 12 to 24 hours old also fall into this category

Dirty: An incision undertaken during an operation in which the viscera are perforated or when acute inflammation with pus is encountered during the operation (for example, emergency surgery for faecal peritonitis), and for traumatic wounds where treatment is delayed, and there is faecal contamination or devitalised tissue present.

Early abdominal wound failure. Defined as surgical site infection, surgical site occurrence or abdominal wound dehiscence diagnosed within 30 days postoperatively.

Incisional hernia. Defined by the European Hernia Society as "any abdominal wall gap with or without a bulge in the area of a postoperative scar perceptible or palpable by clinical examination or imaging".

Late abdominal wound failure. Defined as surgical site infection in presence of foreign body material or incisional hernia at one year postoperatively.

SSI: Surgical Site Infection. Defined by the CDC (Centers for Disease Control and Prevention) as infections related to a surgical procedure that occur near the surgical site within 30 days following surgery (or up to 1 year following surgery where synthetic implants are involved).

SSO: Surgical Site Occurrence. Defined as: wound cellulitis, non-healing incisional wound, skin or soft tissue ischemia, skin or soft tissue necrosis, serous wound drainage, stitch abscess, seroma, hematoma, infected or exposed mesh, surgical site infection, abdominal wound dehiscence.

INTRODUCTION

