- 4. What are the effects of SSI prevention measures on the incidence of early and late abdominal wound failure?
- 5. What is the impact of a minimally invasive technique vs. open technique on the incidence of early and late abdominal wound failure?
- 6. What is the impact of early and late abdominal wound failure on the patient?
- 7. What is the impact of early and late abdominal wound failure on the duration of postoperative stay and the number of outpatient visits and unscheduled hospital visits?
- 8. What are the early and late abdominal wound failure associated costs (eg, hospital/ICU stay, unscheduled hospital visits and patient reported expenses)?
- 9. Which risk scores will have the highest predictive value for our primary outcomes within this cohort?

Summary of the cohort study key objectives

Short term:

Assessing the different practices of wound closure and surgical site prevention globally

Assessing the effect of wound closure and surgical site infection prevention practices on the incidence of abdominal wound failure at 30 days.

Longer-term:

Early phase: 30 days to 90 days
Assessing the different practices of abdominal wound closure and surgical site prevention globally and their effect on wound healing, SSI, patient recovery and return to normal function.

Later phase: 90 days to 1 year
The incidence of abdominal wound failure, including the development of incisional hernia.

Overall:

Exploring the relationship between early adverse wound outcomes and longer-term patient-reported incisional hernia occurrence.

Comparison of quality of life for patients with and without wound healing issues and/or incisional hernia.

Key outcome measures

Short term:

Methods of Wound Closure:

- Types and techniques of fascial, subcutaneous and skin closure
- Incidence and types of mesh use
- Use of SSI Prevention measures
- Incidence of abdominal wound failure at 30 days
- Length of postoperative stay
- Reoperations within 30 days
- 30-day mortality
- SSI diagnosis or management requiring ICU admission
- Unplanned readmissions within 30 days
- Need for interventional radiology procedures within 30 days
- Abdominal wound dehiscence within 30 days

Long-term:

Patient-reported outcomes and quality of life from 30 days to 1 year post-operation

At all time points:

- EQ5D-5L
- SF-12

Early phase [wound healing / SSI / return to normal function]: 30 days to 90 days

- Bluebelle wound healing questionnaire at 30 days

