- Patient reported Wound Recovery PROM - outpatient visits, unplanned hospital visits within 90 days, wound healing, return to work, satisfaction with wound at 30 days
- Repeat the Patient reported Wound Recovery PROM at 60 days and 90 days if wound is not fully healed at these time points

Late phase [wound integrity, reintervention, incisional hernia]: 90 days to 1 year

- Clavien Dindo classification at 30 days
- Surgical site occurrences at 30 days
- ESCP Incisional hernia PROM at 90 days, 6 months, 1 year
- HerQles questionnaire at 1 year

STUDY DESIGN

International prospective cohort study.

The study will collect wound closure and SSI prevention measures employed, and short-term clinical outcomes up to 30 days and longer-term patient-reported outcomes.

Study Timelines

- The cohort study, will open within one month of being approved.
- Participating sites must have started recruitment within 3 months of the study being approved.
- The study is anticipated to close to recruitment in mid-2025.

ELIGIBILITY

Hospital inclusion criteria

Any hospital or surgical unit performing elective and/or emergency abdominal general and colorectal surgery.

Participating sites will be expected to recruit at least 10 consecutive eligible patients within a 4-week period.

At hospital level, data completeness of 95% will be required.

Patient eligibility

Inclusion criteria

- Adult patients (age 18 years and above) undergoing general or colorectal surgical procedures
- Elective (planned admission), expedited (within two weeks), or emergency (unplanned admission) surgery.
- General and colorectal procedures using any type of abdominal incision measuring at least 5 cm (including extraction sites).
- Able to give written informed consent

*For those patients who do not speak the national language of the country in which they are recruited for participation, normal hospital policies for translation to facilitate participation will be followed.

Exclusion criteria

- Patients undergoing incisional, ventral, umbilical, and inguinal/femoral hernia repair
- Simultaneous hyperthermic intraperitoneal chemotherapy (HIPEC) and/or cytoreductive surgery
- Stoma reversal without additional laparotomy incision
- Anyone who does not have an email address or who does not have access to the internet or a smart device.

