The patient will be provided with a unique patient identification number by the person discussing the study with them (this is taken from the site-specific WOLVERINE REDCap LINK SHEET provided by the study office). This unique identifier will be recorded on the WOLVERINE PIS. Eligible patients will also be provided with a generic QR code. This QR code and unique identifier will be used by the potential participants to access the REDCap-WOLVERINE system and the consent form.

The potential participant will then be asked to access the online system at a time convenient to them, i.e. they do not need to access the system whilst in hospital. Upon access of the online REDCap system, they will be asked for consent for follow-up.

This unique REDCap ID will be the only identifier used to identify the patient in any correspondence between the coordinating centre and the participating site.

*Participating sites may download the consent form as a PDF if required for the WOLVERINE Site File.

STUDY FOLLOW-UP

Follow-Up Time points

After the baseline visit, there are no further study-specific visits. All study-specific follow-up is conducted via remote reporting.

There are 5 follow-up time points: 30-, 60- AND 90-days post-surgery; 6 months and one year post-surgery.

Short-term follow-up: 30-days post-surgery

- Clinician reported:
 - o Conducted without the need for patient attendance.
 - No specific follow-up visit is mandated for participants.
 - The 30-day post-surgical outcomes form is undertaken by the clinical team, with routinely collected information from patient notes or electronic records, or other routinely collected data sources.
- Patient reported
 - Data is collected remotely from the participant via the WOLVERINE online REDCap system
 - Bluebelle wound healing questionnaire, EQ-5D5L, SF-12, the Patient reported Wound Recovery PROM QoL and the ESCP Incisional Hernia PROM.

Longer-term follow-up

At the 60-days, 90-days, 6-month and 1 year post-operative timepoints, data is collected remotely from the patient only. The following questionnaires will be requested:

- The EQ-5D5L and the SF-12 at each of the 4 timepoints.
- Bluebell wound healing questionnaire at 30 days.
- Patient reported Wound Recovery PROM at 60 days and 90 days.
- ESCP incisional hernia PROM at 3-, 6- and 12-months.
- HerQles questionnaire at 1 year

^{**}There is no clinical team involvement beyond 30-days post-surgery.

COHORT STUDY SCHEDULE OF EVENTS

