		WOLVERINE COHORT STUDY								
		Study entry	Baseline data	After Surgery	30-day follow- up	30-day PROM	60-day PROM ER DATA	90-day PROM	6-month PROM	1-year PROM
Oliveinian	Patient information		√			PROM NO FURTH	CTION AI	JOIT		
Clinician reported audit	Surgery information			>	1	NO COLLE	DAYS			
- all patients	Short-term Complications / reinterventions				✓					
Patient reported cohort	Informed consent	√								
study – only patients	Wound healing questionnaire (Bluebelle)					√				
who provide consent, recorded	Patient reported Wound Recovery PROM					1	√ if wound unhealed	√ if wound unhealed		
via online PROMS system	ESCP incisional hernia PROM							√	1	√
N.B -	HerQles questionnaire									√
IN ADDITIO N to the clinician-reported patient-level audit data	EQ-5D-5L					√	✓	√	√	√
	SF-12					√	√	√	√	√

PROMS targets for:

- 30 days -> 90 days
 - o SSI, wound healing, return to normal function, patient satisfaction
- 90 days -> one year

 wound integrity, reintervention or readmission, incisional hernia, patient satisfaction

PATIENT WITHDRAWAL

Patients are free to withdraw from the study at any point and will be made aware from the beginning of their involvement in the study that they can withdraw at any time. Participants are given details on how to withdraw from the study in the Patient Information Sheet Before the start of each follow up questionnaire patients will be asked if they are happy to continue participating in the study.

Reasons for Withdrawal

Patients are free to withdraw from participation in the study at any time upon request.

An investigator may terminate a study subject's participation in the study if:

- Any medical condition, event or situation occurs such that continued participation in the study would not be in the best interest of the subject.
- The subject meets an exclusion criterion

Other reasons for withdrawal:

Inability to contact the patient

Handling of Subject Withdrawals

If a patient withdraws from the study, then their record on REDCap will be closed and no further data will be collected. All data collected until that timepoint will be retained and these patients will be included in baseline analyses and reports.

SAFETY CONSIDERATIONS

There are no anticipated safety considerations relating to the WOLVERINE study. There is no risk of harm to either patients or investigators.

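### The late-failure part of question 7 has no supporting data for postoperative stay or for visits after day 90, and question 8 is only partly supported for late failure

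*Protocol*

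**What the plan says.** **The questions.** In the Protocol, Aims & Objectives, question 7 concerns the "impact of early and late abdominal wound failure on the duration of postoperative stay and the number of outpatient visits and unscheduled hospital visits". Question 8 asks: "What are the early and late abdominal wound failure associated costs (eg, hospital/ICU stay, unscheduled hospital visits and patient reported expenses". Both take early and late failure together.

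**The exposure.** The definitions list limits early failure to diagnoses in the first 30 days. Late failure is "Defined as surgical site infection in presence of foreign body material or incisional hernia at one year postoperatively".

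**Stay.** Key outcome measures lists length of stay once, under the short-term outcomes. Ethics & Consent and Data Management limit the review of health records to 30 days after surgery. Study Follow-up adds: "There is no clinical team involvement beyond 30-days post-surgery".

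**Visits.** Key outcome measures gives the content of the Wound Recovery PROM as "outpatient visits, unplanned hospital visits within 90 days, wound healing, return to work, satisfaction with wound at 30 days". It is repeated at days 60 and 90 only for wounds that have not healed. The Cohort Study Schedule of Events shows the same condition, while Study Follow-up lists the 60- and 90-day administrations without it. No section schedules this PROM at 6 months or 1 year. The schedule then holds the hernia PROM, EQ-5D-5L and SF-12, with HerQles added at 1 year.

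**Late targets.** Under the schedule, the PROM targets from 90 days to one year are "wound integrity, reintervention or readmission, incisional hernia, patient satisfaction". The synopsis also counts readmissions and reoperations among the patient-reported data.

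**The concern.** An effect on stay or visits can be estimated only if they are recorded after, or at least alongside, the failure said to cause them. For late failure, the recorded stay lies wholly before the defining time point, and named visit recording ends at day 90 at the latest. A comparison of patients with and without late failure on these measures would reflect earlier differences between them, such as shared risk factors or early complications that led to the late failure. It could nevertheless be reported as the burden of late failure.

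The problem lies in the questions and the data-collection schedule. An analysis plan written later can choose a model, but it cannot supply visit or expense data that were never requested.

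**Working it through.** The Protocol gives no figure to reproduce here. The check compares the time windows and does the arithmetic on them.

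**1. Stay against late failure.** The recorded stay runs from day 0 to day 30 at most. Late failure is defined at one year. Even on the most lenient reading, with late failure counted from the day after the early window closes (day 31), no recorded stay comes after it. The time order in this part of question 7 is therefore reversed.

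**2. Days of the year with a named source for visit counts.**

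| Patient | Last scheduled Wound Recovery PROM | Days uncovered | Share of 365 |
|---|---|---|---|
| Wound unhealed at day 90 | day 90 | 365 − 90 = 275 | 275/365 = 75% |
| Wound healed between days 60 and 90 | day 60 | 365 − 60 = 305 | 305/365 = 84% |
| Wound healed by day 60 | day 30 | 365 − 30 = 335 | 335/365 = 92% |

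The PROM is given at 0 of the 2 time points after day 90. A form completed at day 30 can report only 30 days, so the 90-day visit window is reached only in patients who are sent the day-90 form.

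**3. Who is asked.** Under Key outcome measures and the schedule, recording between days 30 and 90 depends on healing. The definition of surgical site occurrence, itself part of early failure, includes a non-healing wound. Patients with early failure are therefore more likely to receive the later forms, and visit counts to day 90 are collected unequally between the groups that question 7 compares. If Study Follow-up is right and there is no healing condition, this step falls away and the 275-day figure applies to everyone.

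**4. Question 8 for late failure.**
- Hospital and ICU stay: length of stay and ICU admission are listed as short-term outcomes only.
- Readmission and reintervention: stated targets to one year, with no instrument named.
- Unscheduled visits: no named source after day 90.
- Patient expenses: no named instrument at any time point.
- Cost analysis: the only one described, under Planned additional analyses, is conditional on feasibility and concerns surgical site infection.

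**The case against.** The strongest reply is that the Protocol does intend to collect late hospital use. The synopsis, the late-phase heading in Key outcome measures and the PROM targets all name readmission, reoperation or reintervention, and the eligibility note says that further procedures will be captured in follow-up. The hernia PROM goes out at 90 days, 6 months and 1 year, and its items are not shown. It may ask about visits or expenses.

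This reply stands in large part. A reader might infer that questions 7 and 8 cannot be answered at all. The documents do not support that, because the early-failure halves have sources: stay, readmission, reoperation and ICU admission, a mandatory review of clinic notes to day 30, and patient-reported visits. A reader might also infer that readmission and repair after day 90 go unrecorded, or that the cost of late failure will be understated. The first conflicts with the stated targets. The second presumes a late-failure cost analysis that the Protocol does not specify.

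Two further limits apply. The listed content of the Wound Recovery PROM includes no readmission, reoperation or expense items, so these cannot be treated as already available to carry forward. How to handle stays cut off at day 30, or failures diagnosed after discharge, belongs in the analysis plan and is not a fault of the Protocol.

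The reply does not repair the time order for stay, and it does not identify a source for visits after day 90 or for expenses. The Protocol describes its findings as hypothesis-generating because selection bias and interaction cannot be fully controlled. That caveat does not cover an outcome recorded before its supposed cause.

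**Conclusion.** The point holds in a limited form. The late-failure part of question 7 is unsupported for postoperative stay. For outpatient and unscheduled visits it has no named source for at least 275 of 365 days (75%), rising to 335 days (92%) where the wound has healed by day 60. For late failure, question 8 is partly supported: readmission and reintervention are targets to one year, while expenses, and visits after day 90, have no named instrument.

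This rests on three assumptions: that stay is taken from the 30-day record, that the healing condition applies as Key outcome measures and the schedule state, and that the hernia PROM does not ask about visits or expenses. If it does ask, the visit and expense gaps shrink or close, and what remains is that the Protocol does not say so. The conclusion on stay does not depend on the last two assumptions.

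These are secondary questions, and the main research question is not affected. The change is still worth making because it is cheap and cannot be made once the data have been collected.

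**What to change.** 1. Remove late failure as a determinant of postoperative stay in question 7.
2. Then choose one of two routes.
   - Add items on outpatient and unscheduled visits, readmission, reoperation and expenses to the questionnaires already sent at 60 and 90 days, 6 months and 1 year. Ask all participants, whatever the state of the wound, with recall since the previous time point. If the hernia PROM already has some of these items, say so and add only the rest.
   - Or restrict the visit and cost parts of questions 7 and 8 to early failure and the observed window. While the healing condition stands, the only visit form scheduled for everyone is the one at day 30.
3. Reconcile Key outcome measures, Study Follow-up and the Schedule of Events on when, and to whom, the Wound Recovery PROM is given.
4. State which instrument collects each target listed for 90 days to one year.

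The first route adds a few items to existing questionnaires and a small burden on participants. The second costs only narrower wording, but gives up the late-failure visit and cost questions.

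### SSI is an objective and PROM target for days 30 to 90, but after day 30 no stated instrument or case definition captures it for all participants

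*Protocol*

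**What the plan says.** **Objective and target.** In the Protocol's summary of key objectives, the early longer-term phase (30 to 90 days) is to assess closure and prevention practices and "their effect on wound healing, SSI, patient recovery and return to normal function". Below the schedule of events, the PROM targets for the same window are "SSI, wound healing, return to normal function, patient satisfaction".

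**Bluebelle.** The key outcome measures list the "Bluebelle wound healing questionnaire at 30 days". The longer-term follow-up list, which covers day 60 onwards, still gives "Bluebell wound healing questionnaire at 30 days". The schedule of events ticks it in the 30-day column only.

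**Wound Recovery PROM.** The key outcome measures describe its content as "outpatient visits, unplanned hospital visits within 90 days, wound healing, return to work, satisfaction with wound at 30 days". They then say: "Repeat the Patient reported Wound Recovery PROM at 60 days and 90 days if wound is not fully healed at these time points". The schedule of events carries the same condition ("if wound unhealed") at days 60 and 90. The longer-term follow-up list gives the day-60 and day-90 repeats with no condition.

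**Clinician data and definition.** Study Follow-up states that the clinical team has no part after day 30. The definitions section, following CDC, limits SSI to 30 days after surgery, extended to one year where a synthetic implant is involved.

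**The concern.** An objective framed over days 30 to 90 needs an instrument that asks about infection in that window, in everyone, and a definition that lets such an infection count. Bluebelle, the wound questionnaire most plausibly meant for this, is completed on the first day of the window and can only look back from there. What follows is generic quality of life, a hernia questionnaire and a wound questionnaire that may reach only patients whose wounds have not healed.

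At stake is the comparison of closure and prevention practices on wound infection after day 30. If the study runs as written, a reported SSI result for days 30 to 90 would either repeat the 30-day finding under another label or rest on a subgroup defined by non-healing, which is itself an outcome. The same gap reaches late abdominal wound failure in the main research question, because that composite includes SSI where foreign material is present, and no instrument is named for it after day 30. An analysis plan could define the outcome more closely but could not recover data that were never collected.

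**Working it through.** The protocol gives no rate, power or event figure for this outcome, so there is nothing to recompute. The check is to set the schedule, the instrument descriptions and the definition side by side.

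**Step 1: sources of information on infection, by contact in the window** (Key outcome measures, Study Follow-up, schedule of events).

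| Source | Day 30 | Day 60 | Day 90 | Infection named in described content? |
|---|---|---|---|---|
| Clinician review | yes | no | no | yes, through 30-day wound failure |
| Bluebelle | yes | no | no | items not shown; the likeliest SSI instrument |
| Wound Recovery PROM | yes | conditional or not, by section | conditional or not, by section | no; items not shown |
| ESCP incisional hernia PROM | sections differ | no | yes | no |
| EQ-5D-5L, SF-12 | yes | yes | yes | no |

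**Step 2: counts.** Bluebelle is given at 1 of the 5 follow-up time points, and at 0 of the 2 points after day 30 in this window. Clinician ascertainment after day 30 is 0 of 2. Instruments at day 60 or day 90 whose described content names infection: 0.

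**Step 3: what the Wound Recovery PROM can add.** Take an infection that begins after day 30.

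- If the wound is still open at day 60 or day 90, the PROM is given. Its described items on healing and unplanned visits are indirect signals of infection. Whether it asks about infection directly cannot be told from the protocol.
- If the infection has resolved and the wound is healed by the next contact, the outcome list and the schedule of events give no wound questionnaire.
- Under the unconditional longer-term follow-up list, both patients would receive it. The three places therefore lead to different data collection.

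**Step 4: the definition.** For a patient without a synthetic implant, an infection arising in days 31 to 90 is not an SSI under the protocol's own definition. For a patient with an implant it is, but no instrument is named to record it.

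**Step 5: combine.** Without an implant, the definition closes at day 30, and clinician review plus Bluebelle cover it up to then. With an implant, the definition stays open but stated ascertainment stops. In neither group does the protocol state how SSI in days 31 to 90 would be recorded.

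**The case against.** The strongest reply has four parts.

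- **The unseen questionnaire.** The Wound Recovery PROM is a wound instrument at days 60 and 90, and its items are not reproduced. A one-line description is not the full content, so an infection item cannot be excluded. This stands. A reader might infer that infection after day 30 is simply not measured, or that 0 of the 60 days from day 31 to day 90 are covered for every participant. The documents do not support either statement: the count is right for Bluebelle and clinician review, but what the Wound Recovery PROM adds is unknown.
- **The definition already fits day 30.** For patients without an implant, clinician review and Bluebelle cover the whole period in which an SSI can be counted. This also stands. What is lost in them is information on later wound problems, not on SSI as defined. It does not rescue the 30-to-90-day wording, which then promises something the definition excludes.
- **The phase headings are loose.** Day 30 lies inside the range, and the late-phase heading (90 days to one year) likewise lists Clavien-Dindo grade and surgical site occurrences at 30 days. SSI may just be the day-30 item of its group. That is a fair reading, but the objective and target are then mislabelled, because 30-day SSI already belongs to the short-term outcome.
- **Limited consequence.** The protocol calls its output hypothesis-generating, and 30-day wound failure has clinician data. This limits the severity but does not remove the mismatch.

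**Conclusion.** The point holds in a bounded form. SSI is promised for days 30 to 90, yet after day 30 no stated instrument or case definition captures it for the whole cohort. Bluebelle is at 0 of the 2 later contacts, clinician ascertainment has ended, and the one remaining wound instrument is not described as recording infection. It is also restricted to unhealed wounds in two places and unrestricted in a third.

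This rests on the described content of the Wound Recovery PROM being a fair summary. If that form does contain an infection item and goes to everyone, most of the measurement gap closes, and what remains is the definition and the contradictory schedule. The number of participants with an implant is not given, so the group in whom a later SSI could be counted cannot be sized. The 30-day SSI outcome is not affected. The point should be corrected; it does not threaten the study's short-term results.

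**What to change.** Choose one of two routes.

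1. **Narrow the wording.** Restate the early-phase objective, the matching outcome heading and the PROM target as SSI to 30 days, leaving healing, recovery and return to function for days 30 to 90. This costs wording only.
2. **Collect the data.** Give a wound-problem questionnaire to all participants at day 60 and day 90, when everyone is already contacted for EQ-5D-5L and SF-12. This could be Bluebelle, if its recall period suits (the protocol does not state it), or the Wound Recovery PROM with an infection item and no healing condition. Report the result as patient-reported wound problems in days 31 to 90, separate from CDC SSI, and count later SSI only in patients with an implant, as the definitions section requires. This costs a REDCap and schedule change and a small added respondent burden.

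Under either route, reconcile the longer-term follow-up list with the outcome list and the schedule of events on whether the Wound Recovery PROM is conditional. Move the day-30 Bluebelle entry out of the list for day 60 onwards. Name how the SSI component of late wound failure is to be ascertained.
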